1. One period in this study was defined as 14 days. The inspection items should be completed within the time window listed in the test process. In case of statutory holidays, the reason for the overwindow can be recorded in advance and recorded in the CRF. In addition to the follow-up in the flow chart, the investigator may increase the examination items or increase the visit frequency based on the clinical condition of the subject.
2. The informed consent form for the screening period should be signed within 28 before treatment, Written informed consent must be obtained before performing any clinical study procedures, except for the existing tumor imaging examination and tumor tissue biopsy within the time limit specified before the first medication. This study allows previously failed subjects to re-screen, re-sign the informed consent form and re-register to obtain a new subject number.
3. Relevant examination of C1D1, such as relevant data within 7 days, does not have to be repeated. The treatment-phase follow-up program needs to be completed before each cycle of treatment.
4. Safety follow-up will be performed 28 ± 7 days after the last dose or before the start of a new antitumor therapy, whichever occurs first. All AEs occurring before the safety follow-up visit should be recorded until remission to level 0-1 or baseline, or follow-up is not required by the investigator for reasonable reasons (such as recovery or improvement) (whichever occurs first). SAEs occurring within 90 days of the last dose or before the subject started the new anticancer therapy (whichever occurred first) were followed up and recorded. If the patient is not due to disease progression, an imaging examination should be performed at this follow-up. If imaging data are available within the 4 weeks before this follow-up, the investigator can evaluate the need for a re-examination.
5. Survival follow-up began after the end of the safety visit period and was called every 3 months to record subject survival until the end of the last subject or the end of the trial.
6. Genetic tests should include routine tests for bowel cancer, such as MSI status (or MMR status), POLE / POLD 1 mutation status, PTEN mutation status, TMB status, RAS and BRAF mutation status, etc.
7. After height and weight screening period, only weight was measured in other stages to calculate body surface area.

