8. Physical examination during treatment, with specified examination items according to clinical symptoms or clinical needs.
9. Peripheral blood tests include: CD3 +, CD4 +, and CD8 + T cell expression levels.
10. Adverse events were collected from the start of treatment, and once the subject had terminated trial treatment, only new or unresolved adverse events related to trial treatment should be recorded.
11. Concomitant medication records Concomitant medication within 28 days of the screening period and during the trial; once a subject interrupted trial treatment, only concomitant medication and concomitant treatment for new or unresolved adverse events related to trial treatment; no concomitant medication due to other disease should be recorded.
12. Quality of life was assessed using the Wexner rating scale, the EORTC QLQ-C30 scale, and the

EORTC-QLQ-CR29 scale.

1. research background

1.1 summary

Colorectal cancer (colorectal cancer, CRC) is one of the most common malignancies. According to the latest data released by the International Agency for Research on Cancer (International Agency for Research on Cancer, IARC), colorectal cancer is the third among all tumors and the second mortality rate, while China has the second incidence rate and the fifth mortality rate^[1-2]. In recent years, with the continuous improvement of people's living standards, the change of dietary habits and structure, and the aging of the population, the incidence and mortality of CRC in China have been increased. Chinese rectal cancer patients in the overall CRC population, higher than 26% in the United States; middle and low rectal cancer is as high as 70% -80% in rectal cancer, and most rectal cancer patients are in local progression^[1-2].

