- 7 Detection of tumor markers: during induction treatment, during synchronous treatment, during consolidation treatment, and before and after surgery
- 8 Thyroid function: after the end of induction therapy / before synchronous chemoradiotherapy, after completion / before consolidation therapy and before surgery
- 9 Peripheral blood test: after induction treatment / before synchronous chemoradiotherapy, after synchronous chemoradiotherapy / before consolidation treatment, before and after surgery
- 10 Enhanced CT scans of chest, abdominal and pelvic areas: after completion of induction therapy / before concurrent chemoradiotherapy, after completion of concurrent chemoradiotherapy / before consolidation therapy, and before and after surgery
- 11 Pelvic MRI: after completion of induction therapy / before concurrent chemoradiotherapy, after completion of concurrent chemoradiotherapy / before consolidation therapy
- 12 Adverse events: Adverse events after initiation of treatment.
- 13 Concomitant medication: Continuous collection.
- 14 Quality of life assessment: collected per cycle

3) After the completion of the treatment

After completion of treatment, patients should be reviewed at the items and time in the table below; until tumor recurrence or at least 2 years. Review beyond the time of the following table can be conducted according to the habits of different centers, with PET / CT if necessary.

project	After the first moon								
	1	3	6	9	12	15	18	21	24
/	/	/	/	/	/	/	/	/	/
symptom	✓	✓	✓	✓	✓	✓	✓	✓	✓
check-up	✓	✓	✓	✓	✓	✓	✓	✓	✓
routine blood test	✓	✓	✓	✓	✓	✓	✓	✓	✓
Blood biochemical	✓	✓	✓	✓	✓	✓	✓	✓	✓
CEA	✓	✓	✓	✓	✓	✓	✓	✓	✓
Peripheral blood detection	✓								
Chest / abdominal / pelvic CT	✓	✓	✓	✓	✓	✓	✓	✓	✓
colonoscope *					✓				✓
Assessment of QoL	✓	✓	✓	✓	✓	✓	✓	✓	✓
Observe the efficacy	✓	✓	✓	✓	✓	✓	✓	✓	✓

* If the lesion is found by colonoscopy, the colonoscopy period can be shortened according to the specific situation.

4) Safety follow-up

Safety follow-up was performed 28 days after the last dose and the trial planned follow-up is as follows:

- 1 weight
- 2 check-up
- 3 ECOG PS Score
- 4 And a 12-lead ECG
- 5 routine blood test
- 6 Blood biochemical
- 7 routine urine test
- 8 coagulation function
- 9 thyroid function
- 10 Enhanced thoracic, abdominal, and pelvic CT scans: Patients who are discontinued due to disease progression do not need further follow-up enhancement

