- 11 Adverse events: Continuous follow-up until adverse event recovery or further observation is not required by the investigator.
- 12 Concomitant medication: Continuous collection until treatment for the adverse event is completed or the investigator.
- 13 Quality of life assessment

5) Survival follow-up

After disease progression, patient survival status was collected every 3 months allowing telephone follow-up.

5) Patient compliance observation

The investigator's responsibility to ensure patient compliance with the trial will be examined by itinerant representatives.

3.8 data collection

All data shall be timely, truthfully and detailed in the medical record register (Case Report Form, CRF) or CRF software. The medical record form should be filled in by special personnel and signed by the project leader. The medical records (CRFs) shall be checked and collected regularly, and recorded according to the time node required by the clinical trial management center of the hospital.

After the clinical trial, the unit shall write the clinical summary report according to the standard requirements.

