3.9 Clinical safety assessment

1) Adverse events

Definition of the adverse events

Adverse event (or adverse experience, AE): any adverse medical event occurring in a subject or clinical subject, not necessarily causally related to treatment.

The AE can therefore be any bad or non-intended signs (e. g., including abnormal laboratory results), symptoms, or transient drug-related disease, which should be considered for medication involvement.

Adverse events occurring both before and after treatment were considered as adverse events according on management needs. Therefore, safety monitoring (reporting adverse events or serious adverse events) should be performed from subject enrollment to the end of

the study. Therefore, adverse events occurring during signing the informed consent and initiation of study treatment were also considered as AEs.

Adverse drug reactions (ADRs): All toxicities and non-intended reactions to the drug related to any dose should be considered as adverse drug reactions (ADRs).

Response to the drug means that there is at least a reasonable possibility of a causal relationship between the drug and the AE, meaning that this relationship cannot be excluded.

Serious Adverse Event (SAE): means all adverse medical events occurring at any drug dose:

- Lead to death
- life-threatening

Note: "serious" and "life threatening" are defined as an adverse event when the subject has the adverse event; rather than an adverse event that the more serious may lead to death.

- Patients require hospitalization or extension of existing hospitalization
- Leading in persistent or significant incapacity / disability
- Congenital malformations or birth defects

Important medical events: important medical events, do medical and scientific appraisal to decide whether to report is appropriate, these important medical events may not immediately life threat or cause death or hospitalization, but may harm subjects or may need interference to prevent the occurrence of the other results, usually should also be considered serious. For example, some adverse events require severe treatment in the emergency room, or management of allergic bronchial asthma at home; malignant fluid or convulsions without hospitalization; drug dependence and abuse, or malignant tumors histologically different from the primary tumor.

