Other events that should be addressed as SAEs: Drug exposure during pregnancy / lactation: In principle, pregnancy and lactation are under the exclusion criteria. If a pregnancy occurs during the study, the patient should immediately withdraw from the study and inform the investigator immediately and follow up the patient throughout the pregnancy and postpartum. Even if the mother and child are completely normal without any adverse events, the consequences should be recorded. Even if the pregnancy is not a SAE, use the SAE report form.

Events that should be handled as SAEs: disease progression.

2) Record and evaluation methods of adverse events

All AEs should be recorded in the appropriate part of the Medical Record Report Form (CRF). SAE report forms (including initiation or follow-up reports) should also be completed.

The following aspects of each event should be recorded in the CRF:

- AEs in medical terms, not as a subject;
- Date of occurrence (start date);
- Octime (start time);
- Recovery date (end date);
- Recovery time (end time).

The grading was assessed by the investigator as defined by NCI-CTC version 5.0.

- Level 1 = mild;
- Level 2 = moderate;
- Level 3 = Heavy;
- Grade 4 = life-threatening or disabling;
- Level 5 = death.

The investigator should assess the causal relationship between the adverse events and the study drug; the decisive factor assessed in the record is the temporal correlation between the AEs and the study drug. The causal relationship between the adverse event and the study drug or study protocol is judged as follows:

- Uncorrelation = no temporal relationship with the study drug (too early, too late or not medication), or a reasonable causal relationship between the AE and another drug, associated disease or environment;
- Impossible = a temporal relationship with study drug, but no reasonable causal relationship between AE and study drug;
- Probably = a reasonable causal relationship between AE and study drug. Lack of withdrawal information (withdrawal information) or unclear;
- It is likely that there is a reasonable causal relationship between AE and study drug. Discontinuation (withdrawal from the drug study) had an effect on the response. No redose to prove;
- Clear / definite = a reasonable causal relationship between AE and study drug. Discontinuation has an effect on response and can occur if readministered when clinically feasible.

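### Note 10 stops recording unrelated adverse events once trial treatment is terminated, against note 4 and section 3.9: a minor conflict that rewording would settle

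*Combined protocol and SAP*

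**What the plan says.** All places are in the combined protocol and SAP.

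- **Flow-chart description, note 10.** AE collection begins with treatment; then, "once the subject had terminated trial treatment, only new or unresolved adverse events related to trial treatment should be recorded".
- **Flow-chart description, note 4.** The safety visit is 28 ± 7 days after the last dose, or before new antitumour therapy if that is sooner. "All AEs occurring before the safety follow-up visit should be recorded until remission to level 0-1 or baseline". A separate clause covers "SAEs occurring within 90 days of the last dose or before the subject started the new anticancer therapy". Neither clause is limited by causality.
- **Section 3.9.** Part 1) defines an AE as "any adverse medical event occurring in a subject or clinical subject, not necessarily causally related to treatment". It runs safety monitoring from enrolment to the end of the study and adds that "adverse events occurring during signing the informed consent and initiation of study treatment were also considered as AEs". Part 2) puts all AEs in the CRF. Part 4) follows any AE to the end of the study.
- **Section 3.7.** Under 2), item 12 reads "Adverse events: Adverse events after initiation of treatment". Under 4), item 11 reads "Adverse events: Continuous follow-up until adverse event recovery or further observation is not required by the investigator".
- **Note 11.** The same related-only limit applies to concomitant medication once trial treatment is interrupted.
- **Section 4.7, 6).** Safety follow-up runs to 30 days after the end of the last cycle.
- **Protocol summary, statistical method (3) D and E.** AEs and serious AEs are to be listed with severity, time of occurrence, duration, treatment and prognosis, and their incidence given as percentages.

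**The concern.** Notes 4 and 10 stand in the same list and both cover the time from the end of treatment to the safety visit. One asks for every AE in that time, the other only for those attributed to treatment. Section 3.9 agrees with note 4.

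Under note 10, the causality judgement decides whether an event is recorded at all, instead of being an attribute of a recorded event. In a single-arm trial there is no comparator against which to check that judgement, and an event set aside as unrelated leaves no AE entry to re-examine. Note 11 then drops its drug treatment as well. The contents of the AE listing for that period would depend on which paragraph the site staff happened to follow.

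**Working it through.** The plan states no figure to reproduce. The check compares the rules and then places the disputed window in time.

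**Rules side by side**

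| Source | Start | Scope after treatment | End |
|---|---|---|---|
| Note 10 | first treatment | related only | not stated |
| Note 4 | not stated | all AEs; SAEs separately | safety visit; SAEs 90 days |
| 3.9 | consent/enrolment | all AEs | end of study |
| 3.7, 2) item 12 | first treatment | – | – |
| 3.7, 4) item 11 | – | no causality limit, but does not say all AEs | recovery, or investigator's decision |
| 4.7, 6) | – | not stated | 30 days after last cycle |

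The direct conflict is note 10 against note 4 and 3.9. Item 11 of 3.7, 4) governs how long an AE is followed, so it is weak support, and the conflict does not need it.

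**Length of the window.** 28 − 7 = 21 to 28 + 7 = 35 days after the last dose.

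**Position of the window under three readings**

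1. *Last dose* is the last neoadjuvant dose. Assume 14-day cycles, radiotherapy from day 29, and consolidation without a gap (3.1.3 gives no interval).
   - Envafolimab falls on days 1 and 15; 29, 43 and 57; 71 and 85.
   - The last of 25 fractions falls on day 29 + 4×7 + 4 = 61.
   - Surgery (3.2) falls on day 61 + 42 = 103 or day 85 + 21 = 106.
   - The safety visit falls on day 85 + 21 = 106 to 85 + 35 = 120.
   - The window therefore ends on post-operative day 0–14 (surgery day 106) or 3–17 (surgery day 103).
2. *Terminated* means early termination (compare 4.6). Only patients who stop early are affected, for 21 to 35 days after their own last dose. Note 4 makes no exception for them.
3. *Trial treatment* includes the two adjuvant mFOLFOX6 cycles of 3.3. They start about 21 days after resection, on day 124–127. At a 14-day interval the second starts on day 138–141. The visit then falls between day 138 + 21 = 159 and day 141 + 35 = 176, well after the early post-operative days. This applies only to patients who receive those cycles.

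**Any-AE percentage.** A related AE counts under either rule, so only patients without one can change the figure. Section 1.2 reports related AEs in 31/32 patients on a similar regimen. Taking that rate as an assumption, 1/32 = 3.1%, and 35 × 1/32 = 1.1 patients. Such a patient moves the figure only if they also had no unrelated AE on treatment and then had one in the window.

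**Start date.** Consent may precede treatment by up to 28 days (note 2, reading its 28 as days). The safety population in 3.10 requires at least one dose of chemotherapy or radiotherapy, so patients never dosed are outside the analysis. What differs is only whether pre-dose events in dosed patients are counted.

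**The case against.** The strongest reply is that the two notes can be read in sequence: note 4 governs up to the safety visit and note 10 afterwards. The flow chart itself is not in the text available, so the visits to which each note attaches cannot be seen. That sequence is sensible and is what the fix adopts. But note 10 takes effect when treatment is terminated, not at the safety visit, and nothing in the text gives note 4 precedence. The conflict remains as written.

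The second reply stands. A reader might infer that the safety endpoint is compromised. The secondary endpoint is named as the incidence of adverse reactions and serious adverse reactions, and 3.9 defines a reaction by a reasonable possibility of a causal link. Note 10 keeps every new or unresolved related event, so that endpoint is essentially preserved. The gap is in the wider AE listing and percentages of the protocol summary.

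It is also fair that note 10 is not alone on the start date. It agrees with 3.7, 2) item 12, and 3.9 is the one that differs.

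**Conclusion.** The conflict is real and minor. If note 10 is followed, non-serious events judged unrelated between the last dose and the safety visit are missing from the AE listing. pCR is unaffected. SAEs are covered to 90 days by note 4, and surgical complications are a separate endpoint. The any-AE percentage probably changes little. The effect on counts by term, grade and timing cannot be quantified from the documents.

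Two stronger inferences are not supported.

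- **That early post-operative events are lost.** This holds only under the first reading, with consolidation following without a gap. It does not hold under the third reading for patients given adjuvant cycles, nor for watch-and-wait patients (3.4), who have no resection.
- **That the any-AE percentage could move by at most 16.2 points.** That figure comes from the lower exact 95% limit of 31/32 (83.8%; 35 × 0.162 = 5.7 patients). A confidence limit is not a maximum. To reach the figure, every patient without a related AE would also need no unrelated AE on treatment and then one in the window.

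**What to change.** - Amend note 10: record all AEs, regardless of causality, up to the note 4 safety visit; apply the related-only limit only after it; record SAEs to 90 days as in note 4.
- Amend note 11 in the same way, so that drug treatment of unrelated AEs is recorded up to that visit.
- Align the end-of-study wording in 3.9 and the 30-day rule in 4.7, 6) with note 4.
- Define *last dose* and *trial treatment*, stating whether adjuvant mFOLFOX6 is included.
- Use consent as the single AE start date in note 10, 3.7 and 3.9, and tabulate pre-dose events separately from treatment-emergent AEs.

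The cost is protocol and CRF wording and slightly more data entry. No visit is added: the safety visit already exists, and 3.9, 6) already assesses AEs at each clinical visit.

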- [20] Aparna Raj Parikh, Jeffrey William Clark, Jennifer Yon-Li Wo, A phase II study of ipilimumab and nivolumab with radiation in microsatellite stable (MSS) metastatic colorectal adenocarcinoma (mCRC). *J Clin Oncol* 37, 2019 (suppl; abstr 3514).
- [21] Tsukada, Yuichiro, et al. "VOLTAGE: Multicenter phase 1b/II study of nivolumab monotherapy and subsequent radical surgery after preoperative chemoradiotherapy with capecitabine in patients with locally advanced rectal cancer." (2018): TPS878-TPS878.
- [22] Osama E.Rahma, et al. ASCO GI 2021. Oral 8.
- [23] Zhang Tao, et al. ASCO GI 2021. Poster 63.
- [24] Fei Wang, et al. ASCO-GI 2023. Poster 134.

2. research contents

To explore and analyze the efficacy and safety of envafolimab combined with chemoradiotherapy in the whole-course neoadjuvant treatment of pMMR / MSS locally advanced rectal cancer.

2.1 fundamental purpose

- Pathological complete response rate (pCR)

2.2 Secondary purpose

- Objective response rate (ORR);
- Clinical complete response rate (cCR);
- Tumor downstaging rate (mrTRG);
- Downstaging rate of tumor pathology;
- Grade of tumor regression (TRG);
- R0 resection rate;
- Anal rate;
- The rate of surgical complications;
- 2-year disease-free survival rate (2-year DFS);
- 2-year overall survival rate (2-year OS);
- Quality of life (including anal sphincter function, bladder function and sexual function);
- Incidence of adverse reactions and serious adverse reactions.

The safety and tolerability of the study protocol will be evaluated according to the incidence and severity of adverse events and graded according to the NCI CTC AE 5.0 standard.

3. The research plan

This topic is a single-arm, single-center, prospective phase II clinical study.

3.1 Whole-course neoadjuvant therapy regimen:

3.1.1 Induction treatment phase (chemotherapy plus immunotherapy for 2 cycles)

- 1 Envafolimab: 200mg, subcutaneous injection, Q2W, 2 cycles (concurrent administration on the first day of chemotherapy).
- 2 mFOLFOX6: Q2W, 2 cycles: oxaliplatin 85mg / m² intravenous infusion for 2h, day 1. Linovorin calcium 400mg / m² was infusion for 2h on day 1. Fluoruracil 400mg / m², Day 1, then 1200mg / (m² · d) 2d, continuous intravenous infusion (total 2400mg / m², 46 to 48 h).

3.1.2 Synchronous chemoradiotherapy phase (3 cycles of long-range chemoradiotherapy combined with immunotherapy)

- 1 Radiotherapy: 50 Gy / 25f, 2 Gy per day, 5 days per week for 5 weeks.

Body position fixation: using prone position, bladder filling, body fixation frame or vacuum bag fixation;

CT scan: before scanning, intravenous injection of contrast agent to develop the intestine, fill the bladder, empty the intestine, collect two sets of CT images of plain scan and enhanced phase (people with contrast allergy can only collect plain scan images);

Radiotherapy equipment: linear accelerator;

Target area and irradiation field: The target area includes rectal primary and lymphatic drainage area. The treatment plan is IMRT radiotherapy design, and the target coverage and normal tissue limit are determined by the radiotherapy doctor according to the specific situation of the patient.

- 2 Capecitabine: 825mg / m², administered orally twice daily, morning and evening (1650mg / m² / d), 5 days per week, concurrent with radiotherapy for a total of 25 days.
- 3 Envafolimab: 200mg, subcutaneous, Q2W, 3 cycles (administered on radiotherapy days 1,15,29).

